6.2. Appendix 2 Changes to Protocol-Planned Analyses

Not applicable.

6.3. Appendix 3 The Per Protocol Immunogenicity population

The Per Protocol Immunogenicity population will include all randomized and vaccinated participants for whom immunogenicity data are available excluding participants with major protocol deviations expected to impact the immunogenicity outcomes and occurring on Day 1 or before.

In addition, samples obtained from participants will be excluded from the analysis set:

- a- after major protocol deviations expected to impact the immunogenicity outcomes and occurring after Day 1,
- b- after missed vaccinations,
- c- on or after natural SARS-CoV-2 infection (if confirmed by molecular testing or non-S-ELISA [or equivalent assay]) occurring during the study after randomization (if applicable),
- d- after other SARS-CoV-2 vaccination outside the study, or
- e- outside pre-defined time windows (Section 5.1.4).

In terms of derivation, the samples to consider for analysis on Per Protocol Immunogenicity must meet the following criteria:

Subject level

- **Crit1:** Must be randomized
- **Crit2:** Must be in FAS

- **Crit7:** No major protocol deviations with impact on immunogenicity on or before day 1 excluding Deviation Categories '85 for sample not in window', '87 for sample not stored properly'

Subject data level

Subject data to be excluded on and after the date of any of the following events:

- **Crit11:** seropositive post-Baseline by N-ELISA (value>LLOQ), if seronegative at baseline (as defined in Section [5.8.4](#))
- **Crit13:** SARS-CoV-2 infection occurring on or after Day 1
- **Crit20:** Major protocol deviations with impact on immunogenicity after day 1 except for deviation categories '85' or '87', which includes
 - **Crit21:** post SARS-CoV-2 viral vaccination outside the study occurring after Day 1
 - **Crit22:** Vacc 2 not in D57 +/- 8 days
 - **Crit23:** no Vacc 2, then exclude samples where the sample date>Day57+8.
 - **Crit24:** Vacc 3 not in D184 +180/-30 days post vacc1 – Groups 1, 2, 3
 - **Crit25:** no Vacc 3 (within 180 days post Day 184), then exclude samples where the sample date>Day184+30 – Groups 1, 2, 3

Vacc 2 refers to the 2nd dose of the primary regimen

Vacc 3 refers to booster

Sample level

Samples to be excluded on the date of deviation for '85' or '87' events:

- Crit30: major protocol deviations with impact on immunogenicity deviation categories '85' or '87', that is
 - **Crit31:** D1 sample not in window
 - **Crit32:** D29 sample not in window
 - **Crit33:** Day 57 sample not in window
 - **Crit41:** D1 sample not stored properly (i.e. protocol deviation '87')
 - **Crit42:** D29 sample not stored properly
 - **Crit43:** Day 57 sample not stored properly

Reference to Vacc 2

- **Crit34:** Day 71 sample compared to date of Vacc2 not in window
- **Crit35:** Day 184 sample compared to date of Vacc1 not in window - Groups 1, 2, 3-
- or Day 184 sample compared to date of Vacc2 not in window - Groups 4, 5, 6-
- **Crit44:** Day 71 sample not stored properly
- **Crit45:** Day 184 sample not stored properly

Reference to Vacc 3=booster

- **Crit36:** D7 or D14 sample post Vacc3 not in window - Groups 1, 2, 3-
- **Crit37:** D184 sample post Vacc3 not in window - Groups 1, 2, 3-
- **Crit46:** D7 or D14 sample post Vacc3 sample not stored properly - Groups 1, 2, 3-
- **Crit47:** D184 sample post Vacc3 sample not stored properly - Groups 1, 2, 3-

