5. Three participants from the Dose Selection Cohort (of the same dose level group, within the same age group, and from the same 2 dose vaccination regimen with 1 or 2 active vaccinations, with placebo administered as a second dose for those in the 1-dose regimen) experience a Grade 3 unsolicited AE of the same type (per medical judgement of the sponsor), that is determined to be related to study vaccine; OR
6. Three participants from the Dose Selection Cohort (of the same dose level group, within the same age group, and from the same 2 dose vaccination regimen (56-day interval) with 1 or 2 active vaccinations, with placebo administered as a second dose for those in the 1-dose regimen) experience a persistent (upon repeat testing) Grade 3 laboratory abnormality related to the same laboratory parameter and considered related to study vaccine; OR
7. Three participants from the Dose Selection Cohort (of the same dose level group, within the same age group, and from the same 2 dose vaccination regimen (56-day interval) with 1 or 2 active vaccinations, with placebo administered as a second dose for those in the 1-dose regimen) experience a Grade 3 solicited AE of the same type, determined to be related to study vaccine, and persisting as Grade 3 for longer than 3 consecutive days (ie, the day of occurrence of the AE is counted as Day 1).
8. One or more cases of suspected TTS, possibly related to the vaccine.

For number 2 and number 6: to assess abnormal laboratory values, the test must be repeated at least once, within 48 hours of the site becoming aware of the abnormal value.

For number 5, number 6, and number 7: after each IDMC review of similar AE, the committee will indicate the conditions under which it requires further notification and review of the subsequent similar AEs.

Note: the occurrence of a study pause in any other ongoing study with Ad26.COV2.S may trigger a study pause in further vaccination in the current study, if considered to be medically relevant. Any subsequent delayed study visits as a result of a delayed vaccination following a study pause are not considered to be protocol violations.

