Study visits, other than screening and visits at which study vaccination is scheduled, may take place at the participant's home by site staff or a trained and delegated HCP if there are travel restrictions in case of an ongoing pandemic and if allowed by local regulations. The PI continues to be responsible for reviewing all protocol-related assessments. If home visits are not allowed by local regulations, procedures and activities may be done by other methods where possible (such as telephone or video conferencing).

Visit Windows

Visit windows are provided in Section 1.3. The participant should be encouraged to come on the exact day planned and use the visit window only if absolutely necessary.

The timings of the post-vaccination visits will be determined relative to the actual day of the corresponding vaccination. If a participant misses a vaccination, the post-vaccination visits will be scheduled using the date that the vaccination was scheduled to take place.

If a vaccination window is missed due to a study pause (see Section 6.8), efforts will be made to still vaccinate the participant, even if out of window. The timings of the post-vaccination visits will be determined relative to the actual day of the vaccination, unless they would overlap with other scheduled visits, in which case the sponsor should be contacted and a case-by-case assessment is to be agreed upon.

Screening

Screening will be performed within 28 days prior to the first study vaccination or on the day of vaccination. If screening is performed on the day of vaccination, Visit 1 and Visit 2 will both occur on Day 1. Screening must be completed, and all eligibility criteria must be fulfilled prior to randomization and vaccination.

Screening may be conducted in part via a sponsor- and IRB/IEC-pre-approved non-study-specific screening consent process, but only if the relevant pre-screening tests are identical to the per protocol screening tests and are within 28 days prior to first vaccination. However, no study-specific procedures, other than these pre-approved pre-screening assessments, will be performed until the participant has signed the study-specific ICF. Participants who test positive on the molecular test or the serological test (antibodies) will be informed of the result by the study site staff. The study-specific ICF date will be entered into the eCRF. The non-study-specific ICF will be considered source data.

Sample Collection and Handling

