9.4.1. General Considerations

Analysis populations are defined in [Section 9.3](#). Planned analyses are defined in [Section 9.5](#).

^a If a participant would be vaccinated out of window due to a study pause, this will not by default be a reason for excluding this participant from the PPI. A sensitivity analysis might also be performed. Further details will be described in the SAP.

For safety and immunogenicity analyses, results will be analyzed by vaccine group and will be performed by age group in adolescents. Immunogenicity subgroup analyses will also be performed by BMI, ethnicity, and other factors as will be described in the SAP.

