4. POPULATIONS (ANALYSIS SETS) FOR ANALYSIS

Analysis Sets	Description
Enrolled	All participants who sign the main ICF.
Randomized	The randomized analysis set includes all participants who were randomized in the study.
Full Analysis Set (FAS)	The Full Analysis Set will include all participants with at least one vaccine administration documented.

Analysis Sets	Description
Per Protocol Immunogenicity Set (PPI) ^a	The Per Protocol Immunogenicity population will include all randomized and vaccinated participants for whom immunogenicity data are available excluding data from participants with major protocol deviations expected to impact the immunogenicity outcomes (see details in Section 6.3). In addition, samples obtained after missed vaccinations, samples obtained from participants after SARS-CoV-2 infection (if confirmed by molecular testing or non-S-ELISA [or equivalent assay]), occurring during the study after randomization (if applicable), after other SARS-CoV-2 vaccination outside the study, and samples obtained outside pre-defined time windows will be excluded from the analysis set (see details in Sections 5.1.4 and 6.3).

^a If a participant is vaccinated out of window due to a study pause, this will not by default be a reason for excluding this participant from the PPI. Participants who were seronegative by local serology finger-prick test on Day 1 prior to study entry but were determined to be seropositive at baseline by central N- or S- serology testing will also be included (as the results from those assessments are not known prior to randomization).

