5.1.4. Visit Windows

Referring to CTP Section 1.3 per protocol visit windows will be taken into account for the analysis, where applicable.

For immunogenicity-related data analysis, the PPI derivation (see details in [Section 6.3](#)) will be based on the rules which follows:

- Samples obtained after a second vaccination administered outside the time window of the planned day +/- 8 days will be excluded; as well as after a booster vaccination administered outside the time window of the planned day -30 days to +180 days (Groups 1-3).
- Samples obtained outside the following pre-defined time windows will also be excluded:
 - Pre-vaccination for sampling planned on vaccination day
 - Sampling planned day after last vaccination +/- 2 days, if the planned day is 7 days after last vaccination (e.g Day 8 post booster vaccination if given per CTP amendment 3)

- Sampling planned day after last vaccination +8 / -4 days, if the planned day is 14 days after last primary regimen vaccination (i.e. 14 days after dose 2)
- Sampling planned day after last vaccination +/- 8 days, if the planned day is 28 days or 56 days after last primary regimen vaccination (i.e. Day 29 and Day 57 post-dose 1)
- Sampling planned day between 10 and 36 days after booster vaccination, if the planned day is 14 or 28 days after booster vaccination (i.e. sampling post booster vaccination, as given per CTP amendment 3 or amendment 4)
- Sampling planned day after last vaccination +/- 30 days, if the planned day >3 months after last vaccination.

Time windows may be redefined prior to unblinding if the number of samples excluded as per the definitions above are too numerous. No time windows apply for Early Exit visit sampling.

The sample closest to the target day (at noon) will be selected, if two or more samples meet the PPI definition in the pre-defined time windows.

If some participants have undergone sampling at different timepoints than those required per CTP amendment 4 because they followed a different CTP amendment version, data from those different timepoints may be presented separately or pooled together with the most appropriate timepoint per CTP amendment 4 (e.g. all samples planned at 14 or 28 days after booster vaccination will be reported together).

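### A second dose that a study pause delays past Day 65 loses its Day 71 sample from the PPI under SAP 5.1.4 and Crit22, although both documents say such a delay is not by default a reason for exclusion

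*SAP*

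**What the plan says.** SAP Section 4, footnote a to the PPI definition: "If a participant is vaccinated out of window due to a study pause, this will not by default be a reason for excluding this participant". The protocol attaches the same rule to its own PPI definition (Section 9.3, with the footnote text printed under 9.4.1) and adds: "A sensitivity analysis might also be performed. Further details will be described in the SAP".

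Two places in the SAP turn the definition into working rules, and neither mentions a pause:

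- Section 5.1.4: "Samples obtained after a second vaccination administered outside the time window of the planned day +/- 8 days will be excluded".
- Section 6.3: Crit22, "Vacc 2 not in D57 +/- 8 days", stands under the instruction "Subject data to be excluded on and after the date of any of the following events". It is an item of Crit20, the criterion for major deviations after Day 1 that affect immunogenicity. Crit24 works the same way for the booster in Groups 1-3, with a window of Day 184 -30/+180 days.

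On conduct, protocol Section 8 (Visit Windows) says that when a pause causes a vaccination window to be missed, "efforts will be made to still vaccinate the participant, even if out of window". Sections 6.1 and 6.8 leave the decision to case-by-case discussion. Section 6.8 also says: "Any subsequent delayed study visits as a result of a delayed vaccination following a study pause are not considered to be protocol violations".

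SAP 5.4.1 sets the primary immunogenicity timepoints at 28 days after dose 1 (Day 29) and 14 days after dose 2 (Day 71). SAP 5.4.3 places the analysis on the PPI.

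**The concern.** The footnote states an intention, and the derivation gives the opposite result for the data that the intention concerns. A programmer works from 6.3, so the derivation would prevail. The protocol left the details and a possible sensitivity analysis to the SAP. The SAP supplies neither, and its Section 6.2 records no change from the protocol-planned analyses.

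A pause is a foreseen event. Under protocol 6.8 a single related SAE or Grade 4 event is enough, and a pause in another Ad26.COV2.S study may trigger one here. Restart needs a written IDMC recommendation and, where required locally, a substantial-amendment request to the authority (protocol 10.3.6). A delay of more than 8 days is therefore plausible. What is at stake is the number of Day 71 values behind the primary immunogenicity summaries of the 2-dose groups, and the samples that follow.

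**Working it through.** **1. The window.** 57 - 8 = 49 and 57 + 8 = 65, so Crit22 keeps post-dose-2 data only for a second dose on Day 49 to 65. The protocol's visit window of -3/+7 is Day 54 to 64. Someone due on Day 57 has 65 - 57 = 8 days of slack. Someone already using the allowance to Day 64 has 1.

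**2. What the footnote can protect.** The subject-level criteria in SAP 6.3 are Crit1 (randomised), Crit2 (in the FAS) and Crit7 (no relevant major deviation on or before Day 1). A late second dose cannot trigger any of them. If the footnote guarded only membership of the PPI, it would guard against nothing. It has content only for data after the late dose, and that is what Crit22 removes.

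**3. One participant followed through.** Take someone in Group 5 whose Day 57 is the first day of a 28-day pause and who is dosed when it lifts.

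- Dose 2 falls on Day 57 + 28 = 85, which is past 65, so Crit22 applies.
- The sample 14 days later, on Day 99, is on time relative to the actual Vacc 2 date and passes Crit34.
- Crit22 removes it anyway, with everything after it. Day 29 stays.

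**4. How many.** Let the pause last L days, let Day 57 dates be spread evenly over A days, and let dosing take place when the pause lifts. A participant due on pause day d (d = 0, 1, ...) is L - d days late and is lost if L - d > 8. That gives L - 8 affected due dates, so the share lost is f = max(0, L - 8)/A. The geometric-mean CI widens on the log scale by 1/sqrt(1 - f). L and A are assumptions, because the documents give neither. Group size is 50.

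| Pause L | A = 300 days | A = 180 days | A = 90 days | CI width factor |
|---|---|---|---|---|
| 8 days or less | 0 | 0 | 0 | 1.00 |
| 14 days | 6/300 = 2.0% (1.0 of 50) | 6/180 = 3.3% (1.7) | 6/90 = 6.7% (3.3) | 1.01 to 1.04 |
| 28 days | 20/300 = 6.7% (3.3) | 20/180 = 11.1% (5.6) | 20/90 = 22.2% (11.1) | 1.04 to 1.13 |
| 56 days | 48/300 = 16.0% (8.0) | 48/180 = 26.7% (13.3) | 48/90 = 53.3% (26.7) | 1.09 to 1.46 |

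The protocol amendment rationale reports slow enrolment, which favours the larger values of A and so the smaller losses.

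**5. Reach.** Crit22, unlike Crit24 and Crit25, is not limited to particular groups. In Groups 1-3 a pause-delayed placebo injection would also remove Day 71 and later samples, including those around the booster (a secondary objective). Their 28-day post-dose-1 result is kept. Crit24 itself matters little, because a booster would have to slip more than 180 days past Day 184.

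**The case against.** **Participant versus data.** The footnote speaks of excluding the participant, whereas Crit22 excludes data, so the wording is not a flat contradiction and the participant stays in the PPI with Day 29. That is correct as far as it goes. Step 2 shows that this reading leaves the footnote without effect.

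**Not a deviation.** Crit22 sits under major deviations, and protocol 6.8 says that pause-delayed visits are not violations, so pause cases could be argued to fall outside Crit20. The argument is open, but Section 5.1.4 excludes the same samples without requiring any deviation.

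**Existing safeguards.** SAP 5.1.4 lets windows be redefined before unblinding if too many samples are lost, and out-of-window samples stay in the FAS analysis (5.8.1). Both soften the problem. The first is discretionary, turns on counts rather than on cause, and must precede unblinding. The second is promised in 5.4.3 only for selected analyses, and the FAS also contains participants infected during the study.

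**Dose interval matters.** SAP 6.11 matches COV3009 comparators on the interval between doses because of its effect on response, and restricts them to a second dose on Day 42 to 79. An open-ended exception would admit longer intervals. This stands, and it is why the exception needs a sensitivity analysis.

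**Stronger readings.** A reader might infer that one pause would wipe out the Day 71 results. The rules do not do that: only participants pushed past Day 65 are affected. A reader might also infer that regimen choice hangs on these samples. SAP Section 3 rests the choice primarily on safety and reactogenicity, Section 5.9.1 says the selection guidelines will not be assessed in this study, and no hypothesis is tested.

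**Conclusion.** The concern holds in a limited form. The PPI footnotes and the derivation must be reconciled, because as written the derivation discards the post-dose-2 samples that the footnote is meant to keep. The loss is confined to participants whose second dose a pause moves past Day 65. Under the assumptions in step 4 that is about 3 to 11 of 50 per group for a 28-day pause, or about 10 to 33 of the 150 in the 2-dose groups. It is none of those due on Day 57 for a pause of 8 days or less. The consequence is fewer values and a wider descriptive interval at a primary timepoint.

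The documents do not report that a Section 6.8 pause delayed any second dose; if none did, no result changes. SAP Section 2 already refers to primary analysis results, so a change now would mainly bear on the final analysis.

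**What to change.** - In SAP 5.1.4 and Crit22, except second doses delayed by a documented study pause. Word Crit24 the same way for consistency, although the effect there is small.
- Flag these participants, and keep timing the Day 71 sample from the actual Vacc 2 date, as Crit34 already does.
- Report their dose intervals, so that any long ones are visible beside the COV3009 comparators.
- Prespecify the PPI immunogenicity analysis with and without them. The protocol footnote already foresees a sensitivity analysis.

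The cost is a few lines of SAP text, one programming flag and one extra table. The downside is a wider spread of dose intervals in the main PPI, which the analysis without these participants addresses. Nothing here changes the dosing window or the decision whether to vaccinate after a pause.

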6.4. Appendix 4 Demographics and Baseline Characteristics

Demographic and baseline variables (Table 8) will be summarized by vaccination schedule and overall for the FAS.

Table 8: Demographic Variables

Categorical Variables	
Sex (male, female)	
Race (American Indian or Alaska Native, Asian, Black or African American, Native Hawaiian or other Pacific Islander, White, Multiple- If multiple race categories are indicated, the Race is recorded as 'Multiple'-)	
Ethnicity (Hispanic or Latino, not Hispanic or Latino, Not Reported, Unknown)	
Country	
Region	
SARS-CoV-2 Serostatus at Baseline (No baseline, Positive, Negative)	
Age group: • ≥ 12 y to ≤ 15 y • ≥ 16 y to ≤ 17 y	Frequency distribution with the number and percentage of participants in each category.

Continuous Variables:	Summary Type
Age (years)	Descriptive statistics (N, mean, standard deviation [SD], median and range [minimum and maximum]).
Weight (kg)	
Height (cm)	
Body Mass Index (BMI) (kg/m^2)	

6.5. Appendix 5 Protocol Deviations

In general, the following list of major protocol deviations may have the potential to impact participants' rights, safety or well-being, or the integrity and/or result of the clinical study. Participants with major protocol deviations will be identified prior to database lock and the participants with major protocol deviations will be summarized by category.

- Developed withdrawal criteria but not withdrawn
- Entered but did not satisfy criteria
- Received a disallowed concomitant treatment
- Received wrong vaccination regimen or incorrect dose
- Other

Major protocol deviations which have a potential impact on immunogenicity will be flagged in the listings.

6.6. Appendix 6 Prior and Concomitant Medications

The analysis of concomitant therapies will be done using the WHO drug coded terms.

For all participants, concomitant therapies associated with an SAE will be collected and recorded in the eCRF from the moment of first vaccination through the end of the study. Concomitant therapies associated with MAAEs will be collected and recorded in the eCRF from the moment of first vaccination until 6 months after 2nd vaccination. Concomitant therapies associated with MAAEs leading to study discontinuation will be recorded in the eCRF during the entire study. The proportion of participants with concomitant medication associated with these SAEs and MAAEs will be tabulated and listed.

For all participants, concomitant therapies such as, but not limited to, analgesic/antipyretic medications and non-steroidal anti-inflammatory drugs, corticosteroids, antihistamines, and vaccinations will be recorded from the moment of first vaccination until 28 days after administration of study vaccine, and thereafter, pre-dose on the day of any subsequent vaccination and for 28 days after that vaccination. The proportion of participants with concomitant medication will be tabulated by period.

For all participants, other concomitant therapies will also be recorded if administered in conjunction with a confirmed COVID-19 case or with new or worsening AEs reported per protocol requirements outlined in CTP Section 6.8. The proportion of participants with concomitant medication associated with these cases will be tabulated and listed.

Based on their start and stop date, concomitant therapies will be reported in each applicable phase. If a concomitant therapy record misses components of its start and/or stop dates (time, day and/or month and/or year):

- In case of partial start or stop dates, the concomitant therapy records will be allocated to periods using the available partial information, without imputations. If, for example, only month and year are available, these will be compared to the month and the year of the periods, and the concomitant therapy record will be allocated to the period(s) where these date parts match. This rule may lead to assignment to multiple periods.
- In case of a completely missing start date, the concomitant therapy will be considered as having started before the trial.
- In case of a completely missing end date, the concomitant therapy will be considered as ongoing at the end of the trial.

There will be special attention to any systemic use of analgesics/antipyretics, started within 8 days following each vaccination (00:00 of day of vaccination + 7 days). Following CMCLASCD (ATC/DD codes) will be used for this: N02A (OPIOIDS) and N02B (OTHER ANALGESICS AND ANTIPYRETICS), M01A (ANTIINFLAMMATORY AND ANTIRHEUMATIC PRODUCTS, NON-STEROIDS) and M01B (ANTIINFLAMMATORY/ANTIRHEUMATIC AGENTS IN COMBINATION). The classes will be added in a footnote in all related tables and listings. For the use of analgesics/antipyretics which are taken on the day of vaccination an

exception is made in case the time is before vaccination. In this case the concomitant medication is also allocated to the post-dose period.

The use of antipyretics with fever will be tabulated and the use of antipyretics on immunogenicity will be tabulated (overall, NSAIDs vs non-NSAIDs).

